3.2 Inclusion Criteria

Subjects must satisfy the following criteria before entering the study:

- Signed informed consent obtained.
- Symptomatic infrainguinal lower extremity occlusive vascular disease (Rutherford category 3, 4, 5 or 6), stable for at least 2 weeks prior to study inclusion.
- Lesions in the superficial femoral artery (SFA), popliteal, or infrapopliteal arteries
- At least one angiographically identifiable infrageniculate artery
- Patients must be poor surgical candidates, indicated by at least one of the following conditions:
 - Absence of venous autologous grafts (that is, lack of a suitable vein to use for bypass)
 - Poor (diffusely diseased or ≤ 1 mm diameter) or no distal vessels available for graft anastomosis
 - High risk of surgical mortality, evidenced by American Society of Anesthesiologists Physical Class 4 or higher
- Have a lesion that is a chronic total occlusion that cannot be crossed with a standard guidewire. NOTE: This can only be determined at the time of the procedure.

3.3 Exclusion Criteria

Potential subjects who meet any of the following criteria will be excluded from participating in the study:

- Age below 18 years
- Pregnancy, or plan to become pregnant
- Participation in another cardiovascular or peripheral vascular study
- Myocardial infarction (MI) in prior month
- Stents at treatment site
- Disorders or allergies precluding use of radiographic contrast
- Renal insufficiency severe enough to contraindicate use of radiographic contrast
- Contraindication to treatment with anticoagulants
- Untreated ipsilateral iliac stenosis $>70\%$
- Inability or unwillingness of the patient to comply with intended examinations.
- Unavailability of required procedural or imaging equipment
- Lesion located in a graft
- Hemodynamically significant arrhythmia or left ventricular ejection fraction $<20\%$
- Life expectancy less than 6 months
- Necrosis necessitating major amputation
- Unwillingness of the patient to be anti-coagulated

4.0 STUDY DEVICE DESCRIPTION

4.1 The RA-308 Excimer Laser System

The RA-308 Excimer Laser System is a self-contained unit that connects to a sterile energy delivery catheter for use in vascular procedure under fluoroscopic guidance. The laser

energy is commanded by a footswitch that connects to a control system to generate and monitor the laser energy pulses.

The laser energy is ultraviolet at 308nm and is delivered to the surgical site by the single-use catheter that is used in conjunction with other catheter and vascular technology to complete the surgical system.

The energy and density of the laser beam is sufficient to ablate tissue within 50µm of the tip. There is no significant off-axis radiation.

The catheter is inserted into a patient's peripheral vasculature through a previously inserted guiding support catheter, allowing the physician to deliver laser energy targeted to a blockage (lesion) in the blood vessel. Laser energy impinged on the blockage ablates, or debulks, the lesion material thus producing a channel through the blockage.

4.2 Excimer Laser for Use in Plaque Photoablation

Refer to the device Instructions for Use for a thorough description of the procedure.

Procedure Description

The excimer laser crossing procedure is performed in the Catheter Laboratory using standard endovascular techniques. Following introduction to the vascular system and diagnosis using fluoroscopy, including determining that a standard guidewire cannot cross the lesion, the following general guidelines are followed:

1. Insert a commercial guide wire to the blockage.
2. Pass an appropriate guiding catheter (support catheter) over the wire to the lesion. (Steps 1 & 2 can be reversed depending on physician choice.)
3. Remove the guide wire if one fails to cross the CTO or if, at the physician's discretion, angiographic factors determine that a guide wire should not be used because of the presence of a rounded or eccentric stump might bias the guide to a subintimal route, or other complicating factor.
4. Save the initial guide wire and insert the laser catheter and perform a stepwise crossing of the lesion.
5. Cross the CTO with the laser catheter following the step-by-step procedure in the instructions for use.
6. Exchange the laser catheter with the previous wire or another wire.
7. Remove the guide catheter leaving the guide wire in place and, at the physician's discretion, insert other endovascular devices to enhance blood flow.

5.0 STUDY EVALUATIONS

5.1 Overview

The visit schedule and procedures required by this protocol are summarized below:

Event	Screening (Visit 1)	Procedure (Visit 2)	Follow-Up
		Day 0	≥30 Days
Demographics and Medical History Review	X		
Ankle-Brachial Index (ABI)	X		As needed
Rutherford Classification	X		
Angiography		X	
Crossing Procedure		X	
Device-Related Safety Data		As needed	As needed
Doppler Ultrasound			As needed

5.2 Screening

Prior to any study-specific tests or procedure, the benefits and risks of the study must be explained and written informed consent must be obtained from the subject.

The following tests and activities must be performed to verify eligibility:

- Documentation of subject demographic information
- Documentation of relevant medical history
- Rutherford classification
- Review of all inclusion/exclusion criteria to confirm subject eligibility

5.3 Procedure

The following information will be collected for study subjects:

- Pre-laser treatment stenotic assessment using angiography
- Laser treatment procedure time
- Post-laser treatment stenotic assessment using angiography
- Adjunctive procedures, if any, as recommended by the physician
- The duration of lasing
- Device related safety data

5.4 Follow-Up (≥30 days)

The following information may be collected:

- Ankle-brachial index
- Rutherford classification
- Device-related safety data
- Auscultation
- Doppler ultrasound
- Any other relevant information provided by the patient

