2.2.1 Outcome Measures

Procedural success, defined as crossing the target lesion based on angiographic analysis. Crossing the target lesion is defined as successfully placing any endovascular device distal to the occlusion.

No device related major adverse events

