6.6 Data Analysis

The categorical data will be summarized descriptively with frequencies along with the associated percentages. The continuous variables will be summarized by number of subjects, mean, median, standard deviation, minimum and maximum.

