6.6.1 Adverse Events

The number of subjects with at least one adverse event will be tabulated.
 The number of subjects and the number of adverse events will be tabulated by severity and causality and relationship to the treatment procedure.

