8.0 ADVERSE DEVICE EVENTS

8.1 Definition

An adverse event is any untoward medical occurrence in a clinical investigation subject administered the medical device and which does not necessarily have a causal relationship with the treatment. An adverse event can therefore be any unfavorable and unintended sign (including an abnormal laboratory finding), symptom, or disease temporally associated with the use of the device, whether or not the event is considered causally related to the use of the device.

Any worsening of a pre-existing condition or illness is considered an adverse event. Laboratory abnormalities and changes in vital signs are considered to be adverse events only if they result in discontinuation from the study, necessitate therapeutic medical intervention, and/or if the investigator considers them to be adverse events.

For adverse events to be considered sporadic or intermittent, the events must be similar in nature and severity.

Elective procedures/surgeries that occur during the study will not be considered adverse events.

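### Safety collection is worded as device-related only and nothing is required after Day 0, while 6.6.1 tabulates adverse events of any cause and the safety outcome has no time window

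*Combined protocol and SAP*

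**What the plan says.** **What is to be collected.** In 5.3 the procedure-day list includes "Device related safety data". The safety row of the schedule, in the synopsis and again in 5.1, reads "Device-Related Safety Data" and is marked as needed both on Day 0 and at 30 days or later. The 5.4 list also limits its safety item to device-related data. It adds an open item for other relevant information that the patient offers.

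**What is defined and tabulated.** Section 8.1 counts an event as adverse "whether or not the event is considered causally related to the use of the device". Section 6.6.1 states "The number of subjects with at least one adverse event will be tabulated" and "The number of subjects and the number of adverse events will be tabulated by severity and causality and relationship to the treatment procedure". Section 6.6 adds "The categorical data will be summarized descriptively with frequencies along with the associated percentages", without naming the denominator for safety.

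**What is required after the procedure.** Section 5.4 is introduced by "The following information may be collected". Section 2.1 places follow-up at the end-of-procedure angiogram, treats anything later as possibly unnecessary, and lists ways in which it can be done. The follow-up column starts at 30 days and has no end.

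**What the outcome is.** Section 2.2.1 and the synopsis give two outcome measures. One is crossing success. The other is "No device related major adverse events", with no period attached and no hypothesis test in section 6.

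**The concern.** There are two separate gaps.

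The first is scope. A table split by causality needs the unrelated events on record as well as the related ones. If a site records only what the collection rules name, the unrelated category is incomplete, the count of subjects with any event is too low, and nobody can later review whether an event was rightly called unrelated.

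The second is ascertainment. The safety outcome is the absence of something. After the procedure, an absence can arise because no event occurred or because nobody looked, and the plan requires no observation that would separate the two. Section 7.2 lists in-hospital complications such as re-occlusion, renal failure and pseudoaneurysm, and serious events such as re-intervention, bypass surgery and major amputation. All of these can appear after the final angiogram. Because no section asks for the number of subjects observed after Day 0, a reader of the report could not tell few events from few observations.

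**Working it through.** **Step 1. Set the passages side by side.**

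| Question | Collection rules (synopsis schedule, 5.1, 5.3, 5.4) | Definition and analysis (8.1, 6.6.1, 2.2.1) |
|---|---|---|
| Which events? | Device-related safety data | Any cause; tabulated by causality and by relationship to the procedure |
| On Day 0? | Required in 5.3; as needed in the schedules | Counted |
| After Day 0? | Optional in 5.4; as needed in the schedules | Outcome has no time limit |
| Over which subjects? | Not stated | Percentages requested; denominator not stated |

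The first row is a mismatch of scope. The third is an outcome with no required observation behind it once the procedure is over. Neither finding depends on a number.

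**Step 2. Look for a plan figure to reproduce.** There is none for safety: no expected event rate, no precision target, no test. The sizing in 6.5 concerns crossing success only and is unaffected.

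**Step 3. Illustrate the size.** The only input from the documents is the maximum of 50 subjects. Event rate, share of events on Day 0, later capture and number observed are all assumptions.

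*What zero events can exclude.* With zero events among m subjects actually observed, the one-sided 95% upper bound on the event rate is 1 − 0.05^(1/m).

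- m = 50: 1 − 0.05^(1/50) = 5.8%
- m = 25: 1 − 0.05^(1/25) = 11.3%
- m = 12: 1 − 0.05^(1/12) = 22.1%

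For events after Day 0, m is the number observed after Day 0, which the plan does not fix.

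*How easily events go unrecorded.* Let r be the true proportion of subjects with a device-related major event, d the share of such events on Day 0 (all assumed captured), and c the fraction of later events captured. Overall capture is a = d + (1 − d)c. The chance of no recorded event in 50 independent subjects is (1 − r·a)^50.

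| d | c | a | r = 5% | r = 10% |
|---|---|---|---|---|
| any | 1 | 1 | 0.95^50 = 7.7% | 0.90^50 = 0.5% |
| 0.75 | 0.5 | 0.75 + 0.25 × 0.5 = 0.875 | 0.95625^50 = 10.7% | 0.9125^50 = 1.0% |
| 0.50 | 0.5 | 0.50 + 0.50 × 0.5 = 0.75 | 0.9625^50 = 14.8% | 0.925^50 = 2.0% |
| 0.50 | 0 | 0.50 | 0.975^50 = 28.2% | 0.95^50 = 7.7% |

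With partial later capture the shift is modest. It is large only in the last row, where no later event is captured.

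**The case against.** The strongest reply on scope is that collection detail normally sits in the case report forms. Appendix B is only a title page in the available text, and some other pages were removed. Sections 8.1 and 6.6.1 read together point towards recording events of any cause, so the device-related wording may be loose shorthand. Section 8 itself has a heading about device events over an all-cause definition. This stands as a limit. If an all-cause form exists, the scope gap becomes a matter of wording and cross-reference. A form would not, however, make the optional follow-up in 5.4 mandatory.

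On ascertainment, the sponsor can say that 2.1 gives reasons. Crossing is settled at the procedure, and later results depend on the adjunct treatment, so a late event is hard to attribute to a crossing device. The attribution point has some force. But 2.1 argues about measuring adjunct effectiveness, including its ethical worry about 30-day follow-up, and does not discuss recording harms. Section 7.2 says that use of the device may contribute to the listed events.

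There is also real capture outside the schedule. Section 5.3 requires Day 0 safety data and a post-laser angiogram. Section 8.2 refers to an SAE reporting system. Hospital records are source documents under 11.1, and the monitor may review subject records under 11.3. Appendix C, item 13, obliges the researcher to inform the committee of serious events. These make zero later capture an extreme case, but none is a scheduled observation of every subject over a stated period.

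Three stronger readings are tempting and are not supported:

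- *That sites must judge relatedness before recording an event.* No passage sets that order; it is only what the device-related wording would lead to if followed literally.
- *That percentages will be taken over followed subjects only, so that a Day 0 event could drop out.* No passage proposes that denominator; the plan is silent on it.
- *That the safety outcome is meaningless.* Procedure-day harms are covered by mandatory collection.

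**Conclusion.** The point holds in two parts.

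First, the visible collection wording is narrower than the adverse-event definition and the planned table. The main effect is on the unrelated category of that table. Because the stated outcome is itself limited to device-related events, this part reaches the outcome only where a relatedness judgement cannot be checked afterwards. It is conditional on the unseen case report forms.

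Second, no safety observation is required after Day 0 although the outcome has no time limit and the plan's own risk list includes later harms. This is the weightier part, and it applies to device-related events as well. A report of no device-related major events after the procedure could not be interpreted without knowing how many subjects were checked and for how long.

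The size cannot be derived from the documents. The percentages above rest wholly on assumed rates, timing and capture, and show direction only. The crossing test and its sample size are untouched. The change should be made; confidence is medium, because relevant pages were not available.

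**What to change.** 1. In the synopsis schedule, 5.1, 5.3 and 5.4, replace the device-related safety item with all adverse events as defined in 8.1, with relatedness assigned to each recorded event. If the case report forms already do this, refer to them in the protocol.
2. In the synopsis and 2.2.1, state the period that the safety outcome covers.
3. In the schedules and 5.4, require one safety ascertainment per treated subject for that period, by call or chart check. ABI and Doppler can stay optional, so the reasoning in 2.1 about adjunct therapy is not disturbed.
4. In 6.6.1, report the safety outcome over all treated subjects and show beside it the number ascertained for the full period.

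Optional: an exact confidence interval for the event proportion, a supporting summary of the subjects followed, and a clerical alignment of the Day 0 entry in the schedules with 5.3.

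The cost is wording in a few sections and at most 50 calls or chart checks. The downside is slight site effort and a probably higher reported event count, including events unrelated to the device.

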6.0 STATISTICAL METHODS

6.1 Primary Objective

The primary objective of this study is to demonstrate that the Ra device meets its performance goal of a success rate in crossing vascular lesions of at least 65%. A study of the predicate device observed 37 successes in a trial of 47 patients, or a 79% success rate with a 95% confidence interval of 65-88% (Wilson score interval). The performance goal for the Ra device is thus set to be a success rate of at least 65% and the primary objective is to show that the Ra device exceeds this performance goal in a single-arm multi-site pivotal trial. Crossing success rate will be a binary endpoint, where successful crossing of a lesion is defined as crossing the target lesion based on angiographic analysis.

6.2 Statistical Methodology

Primary Objective Test

The primary objective will be tested with a one-sided exact binomial test using a significance level of 0.025.

6.3 Hypothesis

The following null hypothesis will be tested with an overall significance level of 0.025

$$H_0: p \leq 65\%$$

where p is the Ra device crossing success rate. The alternative hypothesis is:

$$H_a: p > 65\%$$

6.4 Study Design

This study will be a non-randomized, single arm, prospective, multi-site clinical trial. The primary effectiveness endpoint will be evaluated using a one-sided test comparing the Ra device crossing success rate to the performance goal of 65%. The lower 95% confidence interval for the success rate of the predicate device was 65%.

6.5 Sample Size Rationale

The required number of subjects to achieve 80% probability to demonstrate the Ra device meets the performance goal when the true success rate is 97% was calculated in the Power Analysis of One Proportion Procedure of NCSS Power Analysis Statistical Software (PASS), Version 14. A 97% success rate was observed in a trial of 78 patients using a similar device (Visona 1998). A sample size of 14 patients yields a 94% probability of meeting the PG of 65% crossing success when the true Ra device rate is 97%; the study will conclude that the PG has been met if 13 or more of the 14 patients are successes. A sample size of 50 patients yields a 99.99% probability of meeting the PG; the study will conclude that the PG has been met if 40 or more of the 50 patients are successes.

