APPENDIX A: Informed Consent

APPENDIX B: Case Report Forms

APPENDIX C: Declaration of Helsinki

A Prospective, Multi Center Pilot Study Evaluating Plaque Photoablation Using the RA-308 Excimer Laser in Subjects with Symptomatic Infrainguinal Lower Extremity Vascular Disease

SYNOPSIS

- Study Objective** To evaluate the safety and efficacy of the RA-308 Excimer Laser System and DABRA Catheter for treating subjects with symptomatic infrainguinal lower extremity vascular disease with chronic total occlusions that cannot be crossed with standard guide wires.
- Study Device** The RA-308 Excimer Laser System and DABRA 101 Catheter consists of a 308 nanometer wavelength Excimer laser and a fluid filled optical catheter.
- Study Design** A multi-center, prospective, non-randomized, open-label study. The study will be conducted at a minimum of two sites.
- Sample Size** Up to 50 male and female subjects will be enrolled.
- Outcome Measures** Procedural success, defined as crossing the target lesion based on angiographic analysis at the time of the procedure. Crossing the target lesion is defined as successfully placing any endovascular device distal to the occlusion.
- No device related major adverse events.

STUDY POPULATION

Inclusion Criteria

Subjects must satisfy the following criteria before entering the study:

- Signed informed consent obtained.
- Symptomatic infrainguinal lower extremity vascular disease (Rutherford category 3, 4, 5 or 6), stable for at least 2 weeks prior to study inclusion.
- Lesions in the superficial femoral artery (SFA), popliteal, infrapopliteal or tibial arteries
- At least one angiographically identifiable infrageniculate artery
- Patients must be poor surgical candidates, indicated by at least one of the following conditions:
 - Absence of venous autologous grafts (that is, lack of a suitable vein to use for bypass)
 - Poor (diffusely diseased or ≤ 1 mm diameter) or no distal vessels available for graft anastomosis

- High risk of surgical mortality, evidenced by American Society of Anesthesiologists Physical Class 4 or higher
- Have a lesion that is a chronic total occlusion that cannot be crossed with a standard guidewire. NOTE: This can only be determined at the time of the procedure.

Exclusion Criteria

Potential subjects who meet any of the following criteria will be excluded from participating in the study:

- Age below 18 years
- Pregnancy, or plan to become pregnant

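### The 50-patient, 40-success rule is valid but leaves about a third of the 0.025 level unused; 48 patients with 38 successes gives slightly more power with two fewer patients

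*Combined protocol and SAP*

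**What the plan says.** Section 6.2 specifies a "one-sided exact binomial test using a significance level of 0.025", and section 6.3 sets the null hypothesis at a crossing rate of 65% or less. Section 6.1 takes the 65% from the predicate: "A study of the predicate device observed 37 successes in a trial of 47 patients, or a 79% success rate", whose lower 95% limit becomes the performance goal.

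Section 6.5 aims for 80% power at a true rate of 97%, and gives the source of that rate: "A 97% success rate was observed in a trial of 78 patients using a similar device". It then describes two sizes. With 14 patients, 13 successes are needed and power is given as 94%. With 50 patients, power is given as 99.99% and "the study will conclude that the PG has been met if 40 or more of the 50 patients are successes". Power is stated at no true rate other than 97%.

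The Synopsis treats 50 as a ceiling ("Up to 50 male and female subjects will be enrolled"), and section 2.1 likewise says that 50 can be enrolled.

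**The concern.** An exact binomial test can attain only certain significance levels, so for a fixed nominal level its power rises and falls in a sawtooth as N increases. Some sample sizes use nearly all of the permitted level and others waste part of it. Fifty is one of the wasteful sizes, and a slightly smaller number does better. Section 6.5 does not bring this out, because at 97% every size near 50 has power close to 100%.

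What is at stake is modest. If the device's true crossing rate lies nearer the predicate's 79% than 97%, the chance of meeting the goal depends noticeably on the choice of N and cut-off. Some of that chance is given up in exchange for two additional patients.

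**Working it through.** **Inputs.** Null rate p0 = 0.65 (6.1, 6.3); one-sided level 0.025, exact binomial (6.2); planning rate 0.97 (6.5); predicate rate 37/47 = 0.787 (6.1); rules 13 of 14 and 40 of 50 (6.5); ceiling of 50 (Synopsis).

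**Formula.** For N patients and cut-off r, the chance of declaring success at true rate p is P(X ≥ r) = Σ from x = r to N of C(N, x) pˣ (1 − p)ᴺ⁻ˣ. Size is this sum at p = 0.65. The valid cut-off for a given N is the smallest r with size at or below 0.025.

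**Step 1: reproduce section 6.5.**
- N = 14, r = 13: size 0.0205; power at 97% is 93.6% (stated 94%). A cut-off of 12 would have size 0.0839.
- N = 50, r = 40: size 0.0160; power at 97% is above 99.99% (stated 99.99%). A cut-off of 39 would have size 0.0342.

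Both cut-offs are the smallest valid ones, and both power figures hold.

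**Step 2: unused level.** At N = 50 the unused part is 0.025 − 0.0160 = 0.0090, or 36% of the level. At N = 48 the smallest valid cut-off is 38: size 0.02493 (a cut-off of 37 has size 0.0510). The unused part is 0.00007.

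**Step 3: why 38 of 48 is better at every rate.** Both rules allow the same number of failures: 50 − 40 = 10 and 48 − 38 = 10. The 50-patient rule simply adds two more chances to fail. The two rules disagree only if the first 48 patients meet 38 of 48 and the last two then take the failures above 10, so the power difference is

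P(X₄₈ = 38) × (1 − p²) + P(X₄₈ = 39) × (1 − p)²,

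which is positive for any p strictly between 0 and 1. At p = 37/47: 0.1402 × 0.3803 + 0.1330 × 0.0453 = 0.0533 + 0.0060 = 0.0593.

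**Step 4: size of the gain.**

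| True rate | 40 of 50 | 38 of 48 | Gain (points) |
|---|---|---|---|
| 75% | 26.2% | 31.6% | 5.4 |
| 37/47 (78.7%) | 49.4% | 55.4% | 5.9 |
| 79% | 51.4% | 57.2% | 5.9 |
| 80% | 58.4% | 63.9% | 5.6 |
| 85% | 88.0% | 90.4% | 2.4 |
| 90% | 99.1% | 99.3% | 0.25 |
| 97% | >99.99% | >99.99% | negligible |

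Gains are taken from unrounded values. Scanning N from 30 to 50 with the smallest valid cut-off for each, N = 48 has the highest power at 37/47 and at 85%.

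**Step 5: sensitivity to the number analysed.** Power at 37/47, each N with its own exact cut-off: 46 (37 needed) 47.3%; 47 (38 needed) 44.3%; 48 (38) 55.4%; 49 (39) 52.4%; 50 (40) 49.4%.

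**Step 6: the 14-patient rule alongside.** If success could be declared either at 13 of 14 or, failing that, at the final size, the type I error is P(X₁₄ ≥ 13) + Σ over x ≤ 12 of P(X₁₄ = x) × P(the remaining patients supply the rest), at p = 0.65. With 40 of 50 this is 0.0205 + 0.0129 = 0.0335 (unrounded sum 0.03345). With 38 of 48 it is 0.0412. Both exceed 0.025.

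**Step 7: safety precision.** With no events, the upper two-sided 95% limit is 1 − 0.025^(1/N): 7.1% for N = 50 and 7.4% for N = 48.

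**The case against.** The strongest reply is that nothing in section 6.5 is wrong. It names its alternative, gives a source, sets an 80% target and meets it, and its cut-offs are correct. At 97% the gain is nil, and at 90% it is a quarter of a point. All of that stands, so this cannot be presented as an arithmetic error, and there is no basis for saying that the section conceals anything.

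A reader might also infer that the trial is underpowered, since 40 of 50 is roughly an even chance at the predicate's rate. The documents do not support that as a defect. They use 79% only to derive the goal; the stated alternative is 97%. Nor would 38 of 48 cure it: power there would still be 55% to 57%, and the smallest exact design with 80% power at 79% is 86 patients with 65 successes (size 0.0236, power 82.0%).

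Two further objections shape the remedy. The optimum is fragile: with 47 evaluable, power at 37/47 falls to 44.3%, below the existing rule. And restricting the primary test to the first 48 when 49 or 50 have been treated would discard evaluable patients in an open-label study without independent adjudication of crossing (section 11.0), so it should not be done.

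Finally, 50 is only a ceiling and section 6.2 fixes the test rather than a cut-off, so analysing 48 would already lead to 38. That is fair, but the plan does not choose 48, and section 6.5 names cut-offs only for 14 and 50.

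**Conclusion.** The point holds as an inexpensive design improvement. Under the plan's own test, level and ceiling, 38 of 48 is valid (size 0.0249) and has higher power than 40 of 50 at every true rate strictly between 0 and 1, with two fewer patients. The gain is about 5 to 6 points for true rates of 75% to 80%, 2.4 points at 85%, and immaterial from 90% upwards. It matters only if the device performs well short of the 97% planning rate.

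The conclusion assumes independent patients with a common success probability, one binary result per patient, and exactly 48 evaluable. It does not show that section 6.5 is miscalculated or that the trial must be powered at 79%.

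**What to change.** Before any outcome data are seen, amend section 6.5, the Synopsis and section 2.1 as follows:

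- State one sample size, 48 evaluable subjects, and one success rule, 38 or more (exact one-sided size 0.0249).
- Remove 13 of 14 and 40 of 50 as decision rules. Leaving the 14-patient rule usable beside 38 of 48 would raise the type I error to 0.0412.
- Keep 50 as the enrolment ceiling only so that non-evaluable subjects can be replaced; define evaluable in advance and stop enrolment at 48 evaluable.
- If a different number is analysed, include every evaluable subject and apply the exact cut-off for that number.
- Optionally, report power at 79%, 85% and 90% beside 97%: for 38 of 48, 57.2%, 90.4%, 99.3% and above 99.99%.

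The cost is wording in three places and no added patients. The downsides are a slightly wider safety bound (7.4% instead of 7.1% with no events) and the loss of the gain should only 47 be evaluable.
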